9.3 Informed Consent	13
9.4 Health Insurance Portability and Accountability Act (HIPAA)	14
9.5 Release of Information	14
9.6 Study Documentation	14
9.7 Records Retention and Requirements	14
9.8 Safety Monitoring	14
9.8.1 Data and Safety Monitoring	14
9.8.2 Protocol Violations Reporting and Management	14

9.8.3 Subject Confidentiality/Privacy 15

9.8.4 Adverse Events (AEs) and Serious Adverse Events (SAEs) 15

9.8.5 Definitions of Adverse Event and Serious Adverse Event 15

9.8.6 Non-Reportable Adverse Event and Serious Adverse Events 15

10.0 DATA MANAGEMENT AND PROCEDURES 17

10.1 Data Collection Forms 17

10.2 Data Acquisition and Entry 17

11.0 HUMAN SUBJECTS PROTECTION 18

LIST OF ABBREVIATIONS

AE	Adverse Event
BMI	Body Mass Index
CDRCC	Center for Depression Research and Clinical Care
ERC	Ethics Review Committee
GCP	Good Clinical Practice
IRB	Institutional Review Board
MDD	Major Depressive Disorder
MOST	Multi-Phase Optimization Strategy
MVPA	Moderate-to-Vigorous Physical Activity
SAE	Serious Adverse Event

STUDY SUMMARY

Title	Increasing Physical Activity among Breast Cancer Survivors with Depression
Short Title	Physical Activity in Breast Cancer Survivors with Depression
Protocol Number	122015-072
Phase	N/A
Methodology	Pilot study of a physical activity intervention among breast cancer survivors with depression
Study Duration	25 weeks
Study Center(s)	Single-center, UT Southwestern Center for Depression Research and Clinical Care
Objectives	Evaluate the feasibility of implementing a multi-component physical activity intervention in breast cancer survivors with significant depressive symptoms.
Number of Subjects	50
Diagnosis and Main Inclusion Criteria	Eligible breast cancer survivors between 3 months and 5 years post-treatment. 1) Positive depression screen (PHQ-9 score > 8) or current antidepressant treatment 2) Report <150 minutes of weekly moderate-to-vigorous physical activity (MVPA) on the GPAQ 3) Physically able to engage in physical activity 4) Written and verbal fluency in English.
Statistical Methodology	A total of 50 patients will be enrolled in this pilot study. The primary objective of this study is to determine the feasibility of implementing a multi-component physical activity intervention among breast cancer survivors with depression. A preliminary analysis of changes in physical activity and depressive symptoms will be conducted following the physical activity intervention.

1.0 BACKGROUND

The over 2.9 million breast cancer survivors in the United States face significant post-treatment health burdens. Five-year recurrence rates for Stage I-III breast cancer survivors range from 7-13%¹ and a subset of breast cancer survivors (e.g., BRCA1/2 mutation carriers) may also have increased risks for other cancers.² Breast cancer survivors have significant medical comorbidities, symptom burdens, and late effects that decrease quality of life and affect prognosis.³ Substantial gaps remain in our understanding of how to improve prognosis for this rapidly growing population. Depression and physical inactivity are inter-related, but modifiable, risk factors associated with prognosis among breast cancer survivors. The proposed pilot project will assess the implementation of evidence-based strategies for increasing physical activity among breast cancer survivors. **Successful completion of project aims will result in crucial pilot data to support future grant applications to identify optimal strategies for increasing physical activity in breast cancer survivors.**

Depression and Cancer Prognosis. **Depression is a common comorbidity in breast cancer survivors and an important factor associated with poor prognosis.** Individual studies estimate the prevalence of Major Depressive Disorder (MDD) in breast cancer survivors to range from 10-30%.⁴ When including dysthymia and minor depression, the rates of mood disorders in breast cancer survivors are estimated to be as high as 50%.^{5,6} **More importantly, depressive symptoms are linked to higher rates of mortality among breast cancer survivors.** A recent meta-analysis integrated 76 prospective studies, including those in which depression was assessed prior to cancer diagnosis and those that assessed depression after diagnosis. Results indicated an 18% increase in mortality for breast cancer patients with depression.⁷ Conversely alleviation of depressive symptoms in breast cancer patients is associated with longer survival,⁸ suggesting the importance of evidence-based interventions targeting depression.

Physical Activity and Cancer Prognosis. **Evidence links physical activity and survival in following breast cancer but the role of inflammatory biomarkers in this relationship has not been adequately examined.**⁹ The largest longitudinal studies¹⁰⁻¹⁴ report consistent decreased risk of breast cancer mortality (ranging from 39% to 51%) among physically active breast cancer survivors. These studies also find physical activity associated with a reduced risk of all-cause mortality, ranging from 27% to 56%.

Physical Activity and Depression. **Numerous trials, including our own work described in Section (3.3.2), have assessed the efficacy of aerobic exercise as a treatment for depression.** Meta-analyses summarizing these studies have reported effect sizes ranging from 0.83 to 1.39 which are comparable to effects of antidepressant medications.¹⁵ The effects of exercise on depression specifically among cancer survivors have also been widely examined. A recent meta-analysis¹⁶ identified 15 RCTs that have examined the effect of exercise on depressive symptoms in cancer survivors. This meta-analysis estimated an effect size (Cohen's d) of 0.22, suggesting a small-to-moderate effect of exercise on depressive symptoms in cancer survivors.

2.0 STUDY OBJECTIVES

2.1 Although multiple strategies for increasing physical activity have proven efficacious, little is known about the optimal intervention strategies for breast cancer survivors or how those interventions can be effectively implemented in real-world settings. The proposed pilot project will assess the implementation of evidence based strategies for increasing physical activity among breast cancer survivors. Results from this pilot project will support future grant applications. These future studies will utilize multi-phase optimization strategy (MOST) to identify the optimal combination of intervention strategies to increase physical activity among breast cancer survivors.

Aim 1. Evaluate the feasibility of screening and subject recruitment through targeted mailings to breast cancer survivors using the UT Southwestern cancer registries.

Aim 1A. Assess the percentage of contacted survivors completing online questionnaires.

Aim 1B. Assess the percentage of respondents meeting eligibility criteria (< 150 minutes of physical activity per week and ≥ 8 on the PHQ-9).

Aim 1C. Assess the percentage of eligible respondents enrolled in the physical activity intervention.

Aim 2. Evaluate the feasibility of implementing a multi-component physical activity intervention in breast cancer survivors with significant depressive symptoms.

Aim 2A. Physical activity program compliance.

Aim 2A.a. Assess the percentage of physical activity classes attended

Aim 2A.b. Assess the percentage of days of use of the self-monitoring device

Aim 2B. Participant-reported program satisfaction

Aim 3. Conduct preliminary analysis of changes in physical activity and depressive symptoms following the physical activity intervention.

Hypothesis 1. Participants in the physical activity program will demonstrate increases in physical activity at three and six months

Hypothesis 2. Participants in the active living program will demonstrate decreases in depressive symptoms at three and six months post-baseline.

Cancer Relevance: This project simultaneously targets two factors (depression and inactivity) related to poor outcomes in breast cancer survivors and provide important information on how to effectively address these risk factors in a real-world setting.

3.0 STUDY DESIGN

3.1 Overview of Study Design

The research project is a pilot study to assess the effects of a multi-component intervention in increasing physical activity among breast cancer survivors with depression. Breast cancer survivors listed in the UT Southwestern Simmons Cancer Center cancer registry will be contacted via mail and invited to complete a brief online questionnaire. Those indicating insufficient levels of physical activity and increased depressive symptoms will be invited to participate. The 12-week physical activity intervention will consist of three evidence-based strategies: print-based materials, active living classes, and activity self-monitoring.

3.2 Duration of Study and Study Timeline

Recruitment of participants will begin in February 2016. We aim to recruit a cohort of 10 subjects in per month through June 2016 for a total of 50 subjects.

4.0 STUDY POPULATION

4.1 Inclusion Criteria

- 1) positive depression screen (PHQ-9 score \geq 8) or current antidepressant treatment
- 2) report <150 minutes of weekly moderate-to-vigorous physical activity (MVPA) on the GPAQ
- 3) physically able to engage in physical activity
- 4) written and verbal fluency in English.

4.2 Exclusion Criteria

- 1) medical condition contraindicating physical activity participation
- 2) cognitively unable to give informed consent
- 3) non-English speaking.

4.3 Participant Recruitment and Retention

Based on previously published work utilizing contact of breast cancer survivors from the cancer registry system,¹⁷ we anticipate that approximately one-third (33%) of the contacted survivors (n=150) will return the questionnaire and agree to future contact to learn more about further physical activity interventions. Based on indications of physical activity frequency from the screening questionnaire, we will invite those who meet eligibility criteria (estimated to be at least 33% of respondents [n=50], based on national prevalence of sedentary behavior and depression among breast cancer survivors) to attend an initial in-person screening and baseline assessment session.

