8.0 STATISTICAL ANALYSES

8.1 Primary Analyses

Based on recommendations of Leon et al.,⁴⁰ the Aims 1 and 2 will examine the feasibility of implementing a physical activity intervention for breast cancer survivors. The feasibility of the study will be assessed by the following criteria:

- 1) Screening - the number of subjects screened through the web-based questionnaire and the percentage of those screened who meet program eligibility requirements
- 2) Recruitment - the percentage of screened subjects that are ultimately enrolled
- 3) Intervention Compliance – defined as percentage of weekly exercise does completed by participants randomized to the exercise condition
- 4) Retention – defined as percentage of assessments completed

Consistent with Aim 3, we will conduct a data analysis examining the effects of the intervention on physical activity and depressive symptoms. A mixed-effects repeated measures model will be used to analyze the primary outcome measures (minutes of MVPA and QIDS-C scores). The independent variables in the model will be time (weeks 1, 13, and 25)(within-subjects factor). The model will allow for random slopes and intercepts while all other factors will be fixed effects. The baseline value of the dependent variable will be included as a covariate as will the other potential covariates if needed [age, race, gender, history of depression]. The need for higher order times terms or the transformation $\log(\text{time}+1)$ to obtain a better fitting model will be considered. The goodness of fit of the final model will be investigated. The analysis will use all available data from all randomized patients with at least one post-baseline visit (i.e., modified “intent to treat” sample) and all tests will be two-sided with alpha of .05 used for significance. The hypothesis will be tested by the significance of the time effect main effect. The analysis will be done using SAS Proc Mixed. Statistical analysis will be completed by [name] within the Center for Depression Research and Clinical Care.

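### Is the expected eligible share of at least 33% in section 4.3 too high for the plan's own depression prevalences?

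*Combined protocol and SAP*

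**What the plan says.** Section 4.3 describes a recruitment funnel. It expects that "approximately one-third (33%) of the contacted survivors (n=150) will return the questionnaire and agree to future contact", and that those who then qualify are "estimated to be at least 33% of respondents [n=50], based on national prevalence of sedentary behavior and depression among breast cancer survivors". The Study Summary and section 3.2 set enrolment at 50, at 10 a month from February through June 2016.

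Section 1.0 gives the only depression prevalences in the document. "Individual studies estimate the prevalence of Major Depressive Disorder (MDD) in breast cancer survivors to range from 10-30" per cent. Once dysthymia and minor depression are counted, "the rates of mood disorders in breast cancer survivors are estimated to be as high as 50" per cent.

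On who qualifies, section 3.1 says: "Those indicating insufficient levels of physical activity and increased depressive symptoms will be invited to participate". Section 4.1 requires under 150 minutes of weekly activity together with a PHQ-9 score of 8 or more "or current antidepressant treatment". Section 5.2 screens against all the criteria in 4.1 and 4.2.

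The eligible share is itself an outcome. Aim 1B reads "Assess the percentage of respondents meeting eligibility criteria", and section 8.1 will report "the percentage of those screened who meet program eligibility requirements". Neither sets a value that must be reached.

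**The concern.** Section 4.3 presents one-third as a floor and names only sedentary behavior and depression as its basis. If both conditions must hold, the eligible share cannot exceed the depressed share, whatever the inactivity rate. The whole range quoted for major depression lies below one-third. The broader figure that could support one-third is itself given as a maximum.

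Three things would be at stake:

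- The 50 expected eligible equal the 50 to be enrolled, so there is no room for a lower share or for refusals.
- Because 8.1 gives no criterion, 33% is the only stated expectation for screening yield. A lower observed yield might be reported as poor feasibility when the Background made it plausible.
- The intervention runs as weekly group sessions, so slower recruitment could thin the groups.

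**Working it through.** **Reproducing the plan's figure.** 150 × 1/3 = 50 (150 × 0.33 = 49.5), so the arithmetic in 4.3 is sound. The 150 must be respondents: if it were letters sent, there would be about 50 respondents and about 16 eligible (150 × 0.33 × 0.33 = 16.3). The implied mailing is 150 × 3 = 450 letters.

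**Inputs.** Depressed share *d*: 10%, 30% and 50%, from section 1.0. Inactive share among the depressed, *i*: not in the documents, so assumed at 100%, 80% and two-thirds. Share on antidepressants and not already counted in *d*, *a*: also not in the documents.

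**Step 1: depression and inactivity only.** Eligible = 150 × *d* × *i*.

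| *d* | *i* = 100% | *i* = 80% | *i* = 2/3 |
|---|---|---|---|
| 10% | 15 | 12 | 10 |
| 30% | 45 | 36 | 30 |
| 50% | 75 | 60 | 50 |

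The first two rows never reach 50. The third always does in this grid, and only just at two-thirds inactive.

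**Step 2: depressed share needed for one-third.** *d* = (1/3)/*i*, which gives 33% at *i* = 100%, 37% at 90%, 42% at 80% and 50% at two-thirds. So how high in the 10-50% span *d* must lie depends on an inactivity share that the documents do not give.

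**Step 3: adding the antidepressant route.** The eligible share becomes (*d* + *a*) × *i*, so *a* = (1/3)/*i* − *d*. At *i* = 80%, *d* = 30% needs *a* = 0.417 − 0.30, about 12%, and *d* = 20% needs about 22%. At *i* = 90%, *d* = 30% needs 0.370 − 0.30, about 7%. The ceiling in step 1 therefore does not bind under section 4.1.

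**Step 4: cost if one-third is too high.** Respondents for 50 eligible = 50/(*d* × *i*), and letters = 3 × respondents. With *d* = 30% and *i* = 80% the share is 0.24, which needs 50/0.24 ≈ 208 respondents and about 625 letters. With *i* = two-thirds it is 0.20, which needs 250 respondents and 750 letters. At 30 respondents a month (150 over five months), the eligible number about 7 and 6 a month instead of 10.

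**Step 5: if 33% is exactly right.** The binomial probability of at least 50 eligible among 150 respondents is then 0.496. Further mailing is about an even chance even when the planning figure is correct.

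**Step 6: if nobody mails again.** Suppose only 36 people are eligible and all enrol. Confidence intervals for Aims 2 and 3 widen by a factor of √(50/36) = 1.18. No power claim is broken, because none is made.

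**The case for a change.** The strongest case for a change is that a floor ought to hold at the low end of its inputs, and this one fails across the whole major-depression range. The antidepressant route does not rescue it on paper, because 4.3 does not cite that route, Aim 1B leaves it out of its summary of eligibility, and no usage figure is given. Screening yield is a primary feasibility result, so a yield of 20-24% set beside a stated 33% could be described as a failure. The remedy would also be cheap: a softer word and the inputs shown.

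Part of this stands. The one-third is not derived in the text, the word that makes it a minimum is not supported by section 1.0, and there is no margin between 50 eligible and 50 enrolled.

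The rest is weaker. The major-depression range is the wrong yardstick for a symptom screen at 8 or more; the mood-disorder figure is closer, and one-third lies within it. The respondents are a self-selected group who answered a letter about a physical activity study and agreed to further contact, so a population prevalence does not cap their share, and selection could move it either way. Section 4.3 appeals to national prevalence, section 1.0 to individual studies, and neither names the other as its source. A 20-24% yield is compatible with the Background, but the Background does not make it likely.

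**Conclusion.** The one-third is an unsourced planning assumption, worded more firmly than the document supports. It is neither an arithmetic error nor a demonstrated contradiction.

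No change to the plan is needed. The observed counts replace the assumption: Aim 1B and 8.1 report the eligible percentage whatever was expected, and no success criterion, sample-size calculation or test refers to 33%. The design is a single-arm pilot, and the share enters no estimate. A shortfall is met by sending more letters, and the weekly meeting in 9.8.1 already considers poor recruitment. On the 20-24% yields above, that means roughly 175 to 300 letters beyond the implied 450 (625 − 450 and 750 − 450), before any refusals. Section 7.1 states no minimum group size that slower recruitment would breach.

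This rests on two assumptions: the registry holds enough survivors for a larger mailing, which the documents do not say, and the yield is reported as an observed percentage with its denominator rather than judged against 33%. A sponsor who prefers to write about one-third and show the inputs loses nothing, but the results and conclusions would be the same.

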5.0 STUDY PROCEDURES

5.1 Informed Consent

Interested persons identified as potential participants will be given an explanation of the study and will undergo a brief pre-screening with trained study personnel. Interested and preliminarily eligible participants will begin the informed consent process. Study personnel will explain the details of the study to the potential participant and then give him or her time to read through the informed consent document. Study personnel will then go through the document with the potential participant and answer any questions he or she may have. Potential participants who choose to provide informed consent and sign the informed consent form will then proceed to the screening assessment.

5.2 Screening

Breast cancer survivors listed in the UT Southwestern Simmons Cancer Center cancer registry will be contacted through an informational letter via mail inviting them to participate in the current study. The letter will include information about the current study and directions to complete an online eligibility screening questionnaire. Potential participants will be screened for eligibility based on all inclusion and exclusion criteria, detailed in sections 4.1 and 4.2. All participants who are screened will complete the Demographics Form.

5.3 Baseline

Potential subjects will meet with a trained project interventionist to be assessed for safety of engaging in physical activity, following recommendations identified in the ACSM guidelines.¹⁸ The Physical Activity Readiness Questionnaire (PAR-Q)¹⁹ is a self-report questionnaire designed to assess safety of engaging in physical activity. In addition, lymphedema and pain will be assessed at baseline and throughout the program to ensure participant safety. Subjects will also be instructed to contact their physician to ensure their safety engaging in physical activity.

Study assessments (described in section 6.0) will be conducted at the baseline assessment visit. Participants will complete the PAR-Q to identify potential medical contraindications. Participants indicating potential contraindications to exercise will be instructed to discuss participation with their physician before engaging in physical activity.

Blood samples will be collected at the baseline assessment visit.

5.4 Treatment and Study Intervention

Participants will be enrolled in the physical activity intervention described in sections 7.0 Assessments will be conducted based on the schedule outlined in section 6.0. Qualified, trained, and certified personnel will conduct clinician-rated assessments (all assessments which are not self-report). During the trial, the outcome assessments will be obtained at Weeks 1, 13, and 25. Participants will be asked to wear an accelerometer during Weeks 1, 13 and 25. If the participant is not able to come to the site and (s)he agrees, some assessments and/or visits may be conducted by phone, by mail, or at appropriate off-site locations, and/or on participants' or other off-site computers via the secure study website(s) if access to a computer with internet service is available. Detailed descriptions of the assessments are provided in section 6.0.

5.5 Participant Discontinuation

In order to ensure safety, female participants who become pregnant during the study will be required to discontinue participation in the intervention. Participants may be asked to stop study intervention if any situation arises that, in the investigator's judgment, poses a safety risk.

Participants who must stop the study intervention will still be asked to complete assessment visits as scheduled.

5.6 Participant Remuneration

Participants will receive monetary remuneration for their participation in the trial to compensate for their time, travel arrangements, and the burden of participation. Essential to the study is appropriate support for participants' time and effort contributing to the study. Reimbursement for attending data collection visits will be made based on the following schedule:

- Reimbursements will be made for participants who complete the initial survey.
- Reimbursements will also be made for the assessment visits (Baseline and Weeks 13 and 25).

25 participants who complete the eligibility screening assessments (described in section 6.2.1) will be chosen randomly to receive a \$100 gift card.

Participants will be paid for each eligible visit using a UT Southwestern Greenphire ClinCard, which can be used as a credit or debit card. Participants will also receive instructions on how use the card. In order receive study payments, the participant's name, address, date of birth and Social Security Number (SSN) will be collected by the research staff. All information will be stored in a secure fashion and will be deleted from the UT Southwestern Greenphire ClinCard system once the study has been completed.

